### **9.3 Monitoring of the study**

During the study, an AstraZeneca representative will have regular contacts with the study site, including visits to:

- Provide information and support to the investigator(s);
- Confirm that facilities remain acceptable;
- Confirm that the study site team is adhering to the protocol, that data are being accurately and timely recorded in the eCRFs, biological samples are handled in accordance with the Laboratory Manual, and that study drug accountability checks are being performed.
- Perform source data verification (a comparison of the data in the eCRFs with the patient's medical records at the hospital or practice, and other records relevant to the study) including verification of informed consent of participating patients. This will require direct access to all original records for each patient (eg, clinic charts).
- Ensure withdrawal of informed consent to the use of the patient's biological samples is reported and biological samples are identified and disposed of/destroyed accordingly, and the action is documented, and reported to the patient.

The AstraZeneca representative will be available between visits if the investigator(s) or other staff at the center needs information and advice about the study conduct.

#### **9.3.1 Source data**

Refer to the CSA for location of source data.

### **9.4 Study agreements**

The PI at each center should comply with all the terms, conditions, and obligations of the CSA for this study. In the event of any inconsistency between this CSP and the CSA, the terms of CSP shall prevail with respect to the conduct of the study and the treatment of patients and in all other respects, not relating to study conduct or treatment of patients, the terms of the CSA shall prevail.

Agreements between AstraZeneca and the PI should be in place before any study-related procedures can take place or patients are enrolled.

Prior to a patient's enrollment in the study and any study-related procedures are undertaken, the following should be fulfilled:

- Signed CSA between AstraZeneca and the PI/study center;

- Signed CSP and other agreements between AstraZeneca and the PI/study center;
- Written approval of the study by the IRB;
- Signed and dated Financial Disclosure forms.

#### **9.4.1 Archiving of study documents**

The investigator will follow the principles outlined in the CSA.

### **9.5 Study timetable and end of study**

The end of the study is defined as “the last visit of the last patient undergoing the study.” The end-of-study definition is for the entire study.

The study is expected to start in \_\_\_\_\_ and to end by \_\_\_\_\_.

The study may be terminated at individual centers if the study procedures are not being performed according to GCP, or if recruitment is slow. AstraZeneca may also terminate the entire study prematurely if concerns for safety arise within this study or in any other study with zolmitriptan.

#### **Discontinuation or suspension of the whole study program**

If AstraZeneca decides to prematurely terminate or suspend the study, the PI, sub-investigator, the head of the institution, and regulatory authorities should receive written notification of the reasons for the premature termination or suspension.

The PI/sub-investigator will immediately notify the decision to the patients, give appropriate medical treatment; take necessary measures, and record treatment or measures provided on the source documents.

#### **Completion of the study**

Upon terminating the study, the PI will report in writing the completion of the study to the IRB and AstraZeneca or its representative.

## **10. DATA MANAGEMENT**

Data Management (DM) will be performed by the CRO.

### **10.1 Electronic case report form**

The eCRF and the protocol are both confidential. The eCRF will be created by the CRO and programmed into the eDC system. All sites will need internet access to access the eCRFs and will only have access to data for patients at their own sites. Data management and other co-ordinator teams will have access to data at all sites.

All eCRFs are to be completed by an authorized member of the investigational staff and reviewed and signed by the investigator. All entries, corrections, and alterations are to be made by the responsible investigator or an authorized member of the investigational staff. All eCRFs are to be completed in a manner that ensures accurate interpretation of data.

It is each investigator's responsibility to ensure that all discontinued orders or changes in the study or other medications entered on the patient's eCRF correspond to the entries on the patient's medical records.

The eCRFs for any patient leaving the study should be completed at the time medication is terminated for whatever reason.

The eCRFs must accurately reflect data contained in the patient's records (eg, source documents).

## **10.2 Dataflow**

After data are entered into the eCRF by study sites, autoqueries that are generated by the eDC system should be addressed by sites. Data queries will be raised for inconsistent, impossible, or missing data. All entries to the study database will be available in an audit trail.

Data entered in the eDC system will be immediately saved to a central database and changes tracked to provide an audit trail. When the PI has signed the eCRF electronically as per eCRF instructions, then the patient's data will be locked.

The data collected through third party sources will be obtained and reconciled against study data.

The data will be validated as defined in the DM Plan. Quality control procedures will be applied to each stage of data handling to ensure that all data are reliable and have been processed correctly.

At the monitoring visit, the Study Monitor must perform the Source Data Verification (SDV) of the required fields on completed forms and if there are no open queries, freeze the form. Data management will run manual consistency checks outside of the eDC system and will raise manual queries for sites to address; if the form is frozen, DM will unfreeze to allow sites to amend data. The same process is to be followed by any other groups creating manual queries in the eDC system (eg, for SAE reconciliation). Once all data are entered, SDV is completed on required fields, manual queries and electronic data reconciliation are completed, and all queries closed, then the casebook can be signed. Once the casebook is signed, DM will then lock the casebook so that no amendments can be made.

## **10.3 Database lock**

### **10.3.1 Final analysis**

When all data have been coded, validated, signed and locked, a clean file will be declared. Any treatment revealing data may thereafter be added and the final database will be locked.

Once all patient casebooks are locked, the final data transfer can be sent to statistics. A database lock checklist will also be completed by DM and the programmer to confirm all applicable quality control checks were performed.

### **10.3.2 Interim analysis**

A partial clean file will be declared for data included in the interim analysis.

## **10.4 Coding**

All AEs and medical/surgical histories recorded in the eCRF will be coded using MedDRA. All medications will be classified according to the AstraZeneca Drug Dictionary (AZDD). All coding will be performed by the CRO. The coding will occur outside of the eDC system and will be merged with the clinical datasets sent to statistics.

## **10.5 Investigator site file**

At the beginning of the study, an investigator's Study File will be established at the study center. The investigator/institution is responsible for maintaining the study documents as specified in the guideline for ICH GCP (Committee for Proprietary Medicinal Products [CPMP]/ICH/135/95) and as required by the applicable regulatory requirement(s). The investigator/institution must take measures to prevent accidental or premature destruction of these documents.

## **10.6 SAE reconciliation**

The CRO will perform SAE reconciliation between the CRO Clinical Study database and the AstraZeneca Clinical Patient Safety database.

## **10.7 ECG data**

ECG data will be processed by a central laboratory and the results will be sent electronically to AstraZeneca or its representative.

# **11. EVALUATION AND CALCULATION OF VARIABLES**

## **11.1 Calculation or derivation of efficacy variable(s)**

A patient diary will be used for collecting the patients' self-assessment of headache pain, symptoms, and treatment response. Patients will assess migraine pain severity and rate the intensity as severe (3), moderate (2), mild (1), or none (0). Baseline is defined as the last non-missing pre-treatment value.

### **11.1.1 Pain-free status**

Pain-free status is a reduction in headache pain intensity from severe or moderate at baseline to none at a specific assessment time. Pain-free status is a binary response variable (yes or no).

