At Visit 2, eligible patients with an established diagnosis of migraine (moderate or severe) who have met the criteria for randomization (no response to placebo challenge, headache characteristics consistent with the inclusion criteria, and ability to complete the study diary) will be randomized to zolmitriptan nasal spray 0.5, 2.5, 5 mg, or matching placebo spray to treat a migraine headache. Paper patient diaries will be provided to patients to record the severity of the headache (mild, moderate, or severe). Patients will complete the diary for 24 hours for the migraine headache treated with the study drug, as well as record any AEs and medications taken at any time. Further dosing instructions will also be provided during this visit.

Patients are to treat 1 migraine headache with 1 dose of zolmitriptan nasal spray 0.5, 2.5, 5 mg, or matching placebo within 10 weeks of randomization (Visit 2). Headache response is defined as a reduction in migraine headache pain intensity from severe or moderate at the time of initial treatment to mild or none at a specific assessment time.

Before taking the study drug, patients cannot have:

- Treated headache with other medication;
- Received any triptan, ergotamine or ergot-type medications (eg, dihydroergotamine or methysergide) in the last 24 hours; or
- Used opiates in the last 24 hours.

If headache pain persists after taking the study drug, approved rescue medication, as agreed by the treating physician, is permitted after 2 hours post-study treatment. Triptans and ergots are not allowed as rescue medications. Allowable drugs include non-steroidal anti-inflammatory drugs (NSAIDs), antiemetics, analgesics (eg, opioids), and sedatives. Rescue medications will not be provided by AstraZeneca.

After taking the study drug, patients may not:

- Sleep or nap for 2 hours;

- Use rescue medications for 2 hours;
- Use other triptan or any ergotamine or ergot-type medications (eg, dihydroergotamine or methysergide) for 24 hours.

Patients will be allowed to continue throughout the study on medications normally taken for migraine prophylaxis, or to correct a long-standing condition provided the condition is stable in the investigator's opinion and that this ongoing treatment won't be adversely affected by study participation.

If there is no treatment with study drug within 4 weeks of randomization, patients will return to the study site for the interim visit to review the study dosing instructions.

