## 5. STUDY CONDUCT

### 5.1 Restrictions during the study

The following restrictions apply in this study during the placebo challenge and treatment period:

1. Patients must treat headache within 30 minutes of onset of moderate to severe headache pain reaching moderate or severe intensity.
2. Patients must be completely symptom-free from any previous headache.
3. Patients must initiate treatment of the migraine headache with only the study drug provided. The nasal spray device is for single use and will contain only 1 dose of study drug. If the migraine does not improve from moderate to severe to none or mild pain at 2 hours post dose, the patient has the option to use rescue medication. A 2nd dose of study drug will not be allowed as rescue medication, nor will it be provided. Rescue medications, as determined by the protocol and the investigator, may be taken 2 hours after taking the study drug and may include NSAIDS, anti-emetics, analgesics (eg, opioids), or sedatives. Rescue medication will not be provided by AstraZeneca.
4. Before taking the study drug, patients must not have:
  - Treated this headache with any other medication,
  - Received any ergotamine or ergotamine-like derivative (eg, dihydroergotamine, methysergide) or triptan (5HT1B/1D agonist) in the 24-hour period before treatment with the study drug,
  - Used opiates in the last 24 hours;
5. After taking the study drug, patients must not:
  - Sleep or nap for 2 hours,
  - Use rescue medication within 2 hours of taking the study drug (see above for use of rescue medication),
  - Use an ergotamine or ergotamine-like derivative (eg, dihydroergotamine, methysergide) or non-study triptans (5HT1B/1D agonist) for 24 hours.

Patients will be allowed to continue any medication being taken at the time of entry into the study (other than medication referred to above for the **acute treatment of migraine or**

**restricted medications noted in Section 5.6).** This includes medication normally taken for migraine prophylaxis or medication normally taken to control a long-standing condition, provided it is for a condition that is stable, and in the investigator's opinion, not adversely affected by participation in the study.

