## **6.3 Efficacy**

### **6.3.1 Efficacy variables**

The primary efficacy endpoint is pain-free status at 2 hours post treatment based on headache intensities recorded in the patient diary (see Section [6.5](#)).

The secondary efficacy endpoints (or outcome variables):

- Pain-free status at 15 minutes and at 1, 2, 3, 4, and 24 hours post treatment;
- Headache response at 15 minutes and at 1, 2, 3, 4, and 24 hours post treatment;
- Sustained headache response at 2 hours subsequent to a 1-hour headache response;
- Presence of associated symptoms of photophobia, phonophobia or nausea at 15 minutes and at 1, 2, 3, 4, and 24 hours post treatment;
- Resolution of associated symptoms of photophobia, phonophobia, or nausea at 15 minutes and at 1, 2, 3, 4, and 24 hours post treatment;
- Incidence and time to use of rescue medication up to 24 hours post treatment;
- Ability to perform normal activities at 15 minutes and at 1, 2, 3, 4, and 24 hours post treatment;
- Headache recurrence 2 to 24 hours post treatment;
- Bilateral headache (yes/no) at 15 minutes and at 1, 2, 3, 4, and 24 hours post treatment;
- Intensity increased by movement (yes/no) at 15 minutes and at 1, 2, 3, 4, and 24 hours post treatment.

Pain-free status is a reduction in headache pain intensity from severe or moderate at baseline to none at a specific assessment time. Pain-free status is a binary response variable (yes or no).

Headache response is defined as a reduction in migraine headache pain intensity from severe or moderate at the time of initial treatment to mild or none at a specific assessment time. Headache response is a binary response variable (yes or no).

Sustained headache response is defined as a reduction in migraine headache pain intensity from severe or moderate to mild or none at 1 hour and maintained at 2 hours after study drug treatment.

Time to use of rescue medication starts with the dosing time of the study drug and ends with the first use of rescue medication. If an event has not occurred by the final assessment point, the response is considered censored for the purpose of analysis.

Resolution of associated symptoms of migraine is defined for those patients who have associated symptoms at baseline who are then symptom free at the assessment timepoints. Associated symptoms of migraine are nausea, vomiting, photophobia, and phonophobia.

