### **11.1.2 Headache response**

Headache response is defined as a reduction in migraine headache pain intensity from severe or moderate at the time of initial treatment to mild or none at a specific assessment time. Headache response is a binary response variable (yes or no).

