### **12.2 Methods of statistical analyses**

All statistical comparisons will be based on a 2-sided significance level of  $\alpha=0.05$  unless otherwise specified.

Descriptive statistics will be used to present efficacy and safety variables. For continuous variables, n, mean, standard deviation, median, minimum, and maximum will be presented. For categorical variables, n, frequency, and percentage will be presented.

Two types of datasets, both derived from the FAS, will be used for efficacy analyses: the observed case (OC) dataset and the last observation carried forward (LOCF) dataset. In general, the OC data for a visit will consist of the actual observations recorded for the visit. If missing, the OC data will remain missing – no data imputation will be performed. The LOCF data will be the corresponding OC data or, if that is missing, the last non-missing data carried forward from the most recent preceding assessment time. However, baseline values will not be carried forward for LOCF imputation. Baseline is defined as the last non-missing pre-treatment value. No other data imputation will be performed.

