### **12.2.3 Secondary efficacy variables**

The following secondary efficacy variables will be analyzed for OC and/or LOCF in the FAS:

- Pain-free status at 15 minutes and at 1, 2, 3, 4, and 24 hours post treatment;
- Headache response at 15 minutes and at 1, 2, 3, 4, and 24 hours post treatment;
- Sustained headache response at 2 hours subsequent to a 1-hour headache response;
- Presence of associated symptoms of photophobia, phonophobia, or nausea at 15 minutes and at 1, 2, 3, 4, and 24 hours post treatment;
- Resolution of associated symptoms of photophobia, phonophobia, or nausea at 15 minutes and at 1, 2, 3, 4, and 24 hours post treatment;
- Incidence and time to use of rescue medication up to 24 hours post treatment;
- Ability to perform normal activities at 15 minutes and at 1, 2, 3, 4, and 24 hours post treatment.
- Headache recurrence 2 to 24 hours post treatment;
- Bilateral headache (yes/no) at 15 minutes and at 1, 2, 3, 4, and 24 hours post treatment;
- Intensity increased by movement (yes/no) at 15 minutes and at 1, 2, 3, 4, and 24 hours post treatment.

For the binary secondary efficacy variables, the same logistic regression model as for the analysis of primary efficacy variable will be used. Time to use of rescue medication will be displayed graphically using Kaplan-Meier curves by treatment group. Comparison of treatment doses versus placebo will be based on the Cox proportional hazard model. The secondary endpoints will be analyzed at the 2-sided 5% significance level without any multiplicity correction.

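### At 3, 4 and 24 hours, relief after rescue medication is scored as study-drug success, which is expected to pull these secondary comparisons toward no difference

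*Protocol*

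**What the plan says.** **Definitions.** Section 11.1.1 reads: "Pain-free status is a reduction in headache pain intensity from severe or moderate at baseline to none at a specific assessment time". Section 11.1.2 defines headache response in the same way, with mild or none as the target. Section 11.1.3 does so for resolution of associated symptoms, and Section 11.1.5 takes normal activities from a yes/no diary question. None of these mentions rescue use. Section 6.3.1 repeats the definitions without adding a condition.

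**Times.** The secondary list in Section 12.2.3 includes "Pain-free status at 15 minutes and at 1, 2, 3, 4, and 24 hours post treatment". Section 6.3.1 has the matching entry "Headache response at 15 minutes and at 1, 2, 3, 4, and 24 hours post treatment". Associated symptoms and normal activities are analysed at the same times.

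**Rescue.** Section 5.1 lists among the things a patient must not do after dosing: "Use rescue medication within 2 hours of taking the study drug". After that, rescue opens. Section 3.1 says that it "is permitted after 2 hours post-study treatment", and Sections 5.1 and 5.6 name anti-inflammatories, analgesics including opioids, anti-emetics and sedatives. Section 5.1 offers it when pain has not fallen to mild or none at 2 hours.

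**Related text.** Section 6.5.1 has patients record each rescue drug with its date and time, and gives the 2-hour reading a window of ±20 minutes. Headache recurrence in Section 6.3.1 already counts a need for rescue. Section 3.2 says that readings before and after 2 hours are there to support the primary endpoint. The synopsis describes the secondary tests as descriptive and uncorrected for multiplicity.

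**The concern.** Take a patient with moderate pain at 2 hours who uses an opioid a few minutes later and records no pain at 4 hours. Under Section 11.1.1 that patient is pain-free at 4 hours, and the relief is credited to the assigned arm. The same holds for headache response, symptom resolution and normal activities at 3, 4 and 24 hours.

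This error is not neutral between arms. Rescue goes to patients whose attack has not responded, and an effective dose should leave fewer of them. The less effective arm therefore gains more successes from rescue, and the contrast narrows.

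At stake is the supporting role that Section 3.2 gives to the later readings. A dose that works could look as though its benefit fades after 2 hours, merely because placebo patients were rescued.

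**Working it through.** **1. The plan's own figure.** Section 12.3 gives a placebo rate of 0.18, a difference of 0.11 (so 0.29 on active), 250 evaluable patients per arm, two-sided 0.05, a continuity-corrected chi-square test and 80% power.

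- Corrected difference: 0.11 − 0.5 × (1/250 + 1/250) = 0.106.
- Null standard error, pooled rate 0.235: √(0.235 × 0.765 × 2/250) = 0.0379.
- Alternative standard error: √((0.18 × 0.82 + 0.29 × 0.71)/250) = 0.0376.
- Power = Φ((0.106 − 1.96 × 0.0379)/0.0376) = 80.0%.

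For 250 against 150 the same method gives 67.9%, against a stated 67%. Both figures reproduce. They concern the 2-hour endpoint and are not challenged here.

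**2. Dilution after 2 hours, equal rescue behaviour.** The protocol gives no rates for the later readings, so I assume that 0.18 and 0.29 would be the pain-free rates there without rescue. Let u be the share of non-pain-free patients who take rescue, and s the share of those who become pain-free because of it. Both are assumptions, equal in the two arms.

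- Scored rate: p′ = p + (1 − p)·u·s.
- Scored difference: p₁′ − p₀′ = (p₁ − p₀)(1 − u·s).

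| u | s | placebo | active | difference | odds ratio | power, 250 per arm |
|---|---|---|---|---|---|---|
| 0 | – | 0.180 | 0.290 | 0.110 | 1.86 | 80% |
| 0.2 | 0.2 | 0.213 | 0.318 | 0.106 | 1.73 | 73% |
| 0.4 | 0.4 | 0.311 | 0.404 | 0.092 | 1.50 | 54% |
| 0.6 | 0.6 | 0.475 | 0.546 | 0.070 | 1.33 | 32% |
| 0.8 | 0.6 | 0.574 | 0.631 | 0.057 | 1.27 | 23% |

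For u = s = 0.4: 0.18 + 0.82 × 0.16 = 0.311, 0.29 + 0.71 × 0.16 = 0.404, and 0.11 × 0.84 = 0.092. In this model, scoring rescued patients as non-responders restores the first row. The power column only shows scale, because the trial is not sized for these endpoints.

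**3. Unequal rescue.** Suppose that 30% on placebo and 40% on active are pain-free at 24 hours with no rescue taken (assumed). Then scored rate = that rate + rescue share × relief share.

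- Rescue 25% v 18%, relief 50%: 0.425 v 0.490, difference 0.065.
- Rescue 35% v 22%, relief 60%: 0.510 v 0.532, difference 0.022.
- Rescue 45% v 30%, relief 70%: 0.615 v 0.610, difference −0.005.

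The starting 10 points here already include the difference in rescue use, so these results are not comparable row by row with step 2.

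**4. The 2-hour endpoint.** Only two routes remain: rescue taken early against the rules, or a reading made late in the +20 minute window after rescue. If a share q of non-responders were converted in these ways (assumed), the difference is 0.11 × (1 − q). That is 0.109 at q = 0.5% and 0.108 at q = 2%, with power of 79% and 77%.

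**The case against.** **Analysing what was recorded is a legitimate choice.** Status regardless of rescue is a treatment-policy estimand, and the plan also reports incidence of and time to rescue, so a reader would see differential rescue beside the later rates. This stands as a reason to keep the as-recorded analysis. But the protocol does not say that it chose this estimand, its recurrence definition goes the other way, and Section 3.2 uses the later readings to support a drug effect.

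**The SAP could add a rule.** Section 12 promises one, and it is not at hand. However, Section 11.1 is where the protocol sets its derivations, and as written they credit rescue relief. That is a stated rule, not only missing detail.

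**A reader might infer that the primary result is compromised.** Section 6.3.1 says: "The primary efficacy endpoint is pain-free status at 2 hours post treatment based on headache intensities recorded in the patient diary". Rescue is barred until then. A compliant patient offered rescue under Section 5.1 has already failed at 2 hours; to count as a success, that patient would have to leave the reading blank, take rescue and become pain-free within 20 minutes. The documents do not support more than a small effect.

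**A reader might infer that Section 12.2 forbids scoring rescue users as failures**, because it says "No other data imputation will be performed". That sentence closes a paragraph on missing values. Scoring a recorded reading after rescue as non-response is a derivation rule, so nothing there prevents it.

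**A reader might also extend the point to last observation carried forward**, where a pain-free 1-hour entry fills a missing 2-hour one. That is a separate missing-data question and no part of this point.

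**Conclusion.** The point holds for the 3, 4 and 24 hour readings. The protocol's definitions count relief after rescue as study-drug success, and the expected direction is toward no difference. This assumes that patients still in moderate or severe pain, who are the ones offered rescue, are more numerous in the less effective arm.

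The size is unknown. With equal rescue behaviour, an assumed 0.11 falls to between 0.106 (u·s = 0.04) and 0.057 (u·s = 0.48). A higher rescue share on placebo would shrink it further. A reader might conclude from the last case in step 3 that results could reverse; that is one extreme set of assumed inputs, and with equal u and s the sign cannot change.

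The affected analyses are secondary and descriptive, and the primary endpoint is largely protected. This is a worthwhile correction to the definitions, not a threat to the trial's main conclusion.

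**What to change.** Add a scoring rule to Section 11.1, and mirror it in Section 6.3.1:

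- At any reading after first rescue use, pain-free status, headache response, symptom resolution and ability to perform normal activities are scored as no, and associated symptoms as present.
- The rule includes a 2-hour reading recorded after rescue, whether rescue was early or the reading was late in its window.
- Order is decided from the rescue and assessment times in the diary.
- The as-recorded values are reported as a sensitivity analysis.

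The cost is a few lines of definition and a derivation step; no new data are needed. Absolute response rates become somewhat lower. The endpoint then means relief without rescue, so a patient who would have recovered anyway by 24 hours but took rescue counts as a failure. The change concerns scoring only and leaves the clinical rescue rule as it is.
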